	
replaced in the Monotherapy period, in Cycle 1 or 2, the number of patients will be higher than 34.
 
Analysis sets:
 
There will be two analysis sets
 
• Safety Set: All patients treated with at least one dose of idronoxil will be included in the Safety Set (SS). All analyses of safety, toxicity, and PK will be performed for this set.• Full Analysis Set (FAS): All patients who completed at least one cycle of combination therapy (at any NOX66 dose). 
Analyses of efficacy, tolerability, and biomarkers will be performed for the FAS. Separate summaries may be provided for patients participating in the Dose Escalation and Dose Expansion parts.
 
Safety (Primary analysis):
 
The safety profile will be based on Serious Adverse Events (SAEs), Treatment Emergent Adverse Events (TEAEs), standard clinical laboratory parameters (clinical chemistry, hematology, urinalysis), vital signs measurements, ECG parameters, and physical examination findings.
 
Adverse events (AE) will be coded using the Medical Dictionary for Regulatory Activities and summarized by dose when NOX66 is given alone or in combination with doxorubicin. The number and percentage of patients reporting TEAEs will be calculated overall, by system organ class, and by preferred term for each dose level. Adverse events will also be graded for severity according to the National Cancer Institute Common Terminology Criteria for Adverse Events, Version 5.0.
 
Serious Adverse Events (SAEs) will be summarized separately.
 
Cardiac AEs (including clinically significant abnormalities in ECG rhythm and waveform morphology reported as TEAEs) and changes in echocardiographic parameters will be summarized.
 
Descriptive statistics will be provided for demographics, baseline characteristics, and exposure to treatment by cohort.
 
Univariate summary statistics will be provided by dose group at each visit for quantitative laboratory parameters and vital signs and for the change from baseline in these parameters. For laboratory values and vital signs with defined CTC grades, shift tables will be provided for CTC grades from baseline to end of study and from baseline to worst value on study.
 
Univariate summary statistics will be presented for ECG parameters for the value at each measurement time point and the change from baseline to each measurement time point. A similar analysis will be provided for the worst value of each ECG parameter on study.
 
Findings from physical examinations and ECOG performance status will be summarized by dose of NOX66 given alone or in combination with doxorubicin.
 
Pharmacokinetics (Secondary analysis):
 
Individual blood concentration-time data and blood PK parameters will be summarized using descriptive statistics by dose and sampling time for idronoxil and metabolites. Separate summaries will be provided for PK

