8.1.1 DOSE-ESCALATION

For all dose escalation cohorts, there will be 7 days of monotherapy treatment with NOX66 followed by a 5- day washout period prior to the start of combination cycles of NOX66 and doxorubicin. The purpose of the monotherapy treatment is to evaluate the safety and tolerability of NOX66 when administered alone and as well as single and multiple dose PK of idronoxil.

The dose-escalation part of the study will include three planned Treatment Groups (800, 1200, 1800 mg daily) of 3 patients each. The first 3 patients will be entered at Dose Level 1 and will receive daily doses of NOX66 for 7 days. All of these doses, except for the 1800 mg have been evaluated in 2 previous clinical trials and have been relatively well tolerated as monotherapy for 14 days and in combination with carboplatin for 42 days.

After a rest period of 5 days and if no significant toxicities (DLT equivalent toxicity) have occurred, patients will enter the combination therapy part of the study which will consist of up to 6 x 21-day treatment cycles. Each cycle will consist of 7 days of NOX66 (at the assigned dose), doxorubicin (75 mg/m²) on Day 2 of the 21-day cycle (administered at approximately 1 hour after rectal application of NOX66) and a rest period of 2 weeks.

For the 800 mg and 1200 mg dose levels NOX66 will be administered twice-daily (BID) with a 400 mg or 600 mg suppository, respectively, and the 1800 mg dose level will entail administration of a 600 mg suppository three times daily (TID). In all cohorts, doxorubicin will be given initially at 75 mg/m² as an intravenous infusion over 15 minutes (or as per standard of care). This dose may be reduced to 60 mg/m², at the Investigator's discretion for unacceptable Grade ≥ 2 toxicity. A dose reduction of 50% is recommended if serum bilirubin is 1.2 -3.0 mg/dL prior to a cycle. If serum bilirubin is 3.1-5.0 mg/dL prior to a cycle, a 75% dose reduction of doxorubicin is recommended.

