11.3 STUDY PROCEDURES

[figure not shown]
This study will be conducted in three parts each with screening, treatment and follow up periods as outlined in [Table 2](#). In the Dose Escalation Part, patients receive NOX66 monotherapy followed by NOX66 and doxorubicin combination therapy. In the Dose Expansion Part, patients receive NOX66 and doxorubicin combination therapy only. Patients in each part will be followed post therapy for about 14 months. An overview of phases of the study by period is shown below ([Table 2](#) and [Figure 1](#)).

Table 2 Treatment Periods

	Dose Escalation Only		Dose Escalation & Dose Expansion								
Screening	Monotherapy	Washout	Combination Treatment Cycles [#] 6 Cycles X 21 Days	Follow-Up from C1D1					Month 18 EOS (18 M from C1D1)		
				Month 6 (6 M from C1D1)	Month 9 (9 M from C1D1)	Month 12 (12 M from C1D1)	Month 15 (15 M from C1D1)				
28 days	7 days	5 days	126 days	1.8 M from C6D21	3 M from last f/u	3 M from last f/u	3 M from last f/u	3 M from last f/u			
	12 days		4.2 Months	1.8 Months	3 Months	3 Months	3 Months	3 Months			
1.3 Months			18 Months								
~ 20 Months											

C1D1 = Cycle 1 Day 1; EOS = End of Study; f/u = follow-up, M = month

[#]Each combination therapy cycle is 21 days with NOX66 administered on Days 1-7 at a fixed dose and regimen. On Day 2 doxorubicin is administered intravenously for 15 minutes at 75 mg/m². No treatment is administered on Days 8-21. During the follow-up period, neither NOX66 or doxorubicin is administered, but other approved or investigational medication for sarcoma may be administered.

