11.6.2.12 Month 18 (from Cycle 1 Day 1) - End of Study/Early Termination

- Assess tumor response with CT or MRI, including patients who discontinue the study for progressive disease.
- Measure vital signs (blood pressure, pulse [radial or brachial (to be measured over 30 seconds if performed manually)], respiration rate and body temperature [oral or aural]; Section 11.4.2.1).
- Assess ECOG performance status.
- Collect urine and fasting blood samples for clinical laboratory tests (Section 11.4.2.4).
- Administer questionnaires BPI-SF, EORTC QLQ-C30 and EORTC QLQ-FA12.
- Perform a physical examination (Section 11.4.2.2).
- Review and record concomitant medications.
- Assess and review TEAEs (Section 16).
- Assess overall survival.

Table 4 Schedule of Procedures and Assessments for Three Periods of the Study

Procedure/Assessment	Study Day	Dose Escalation & Dose Expansion	Dose Escalation NOX66 Monotherapy Period							
		Screening	Monotherapy (Days)							Off-treatment Days
		Day -28 to Day -1	1	2	3	4	5	6	7	8
Obtain informed consent		X								
Inclusion/exclusion criteria		X	X							
Medical and surgical history ¹ (including histopathology data and STS grade)		X	X							
Assess disease status (CT and/or MRI) ²		X								X
Vital signs ³		X	X						X	
Physical examination ⁴		X	X						X	
ECOG performance status		X							X	
Hematology, clinical chemistry ⁵		X	X						X	
Urine pregnancy test (WOCBP only)		X	X							
BNP, troponin I			X						X	
Blood for cytokines, chemokines, immunoassays (ENOX2)		X [†]	X [†]						X	
Genetic mutation sample		X [†]	X [†]							
Archival tissue sample (Optional)		X								
Urinalysis		X	X						X	
12-lead ECG ⁶		X	X						X	
Holter monitoring ⁶									X	
Dispense 7-day supply of NOX66			X							
Echocardiography		X								
Administer NOX66 ⁷			X	X	X	X	X	X		
PK samples ⁸			X	X					X	X
Record AEs		X						X		
Prior & concomitant medications		X						X		
Assess dosing compliance ⁹									X	
Brief Pain Inventory (BPI-SF) ¹⁰			X						X	
EORTC QLQ-C30 ¹⁰			X							
EORTC QLQ-FA12 ¹⁰			X						X	
Suppository Acceptance Questionnaire ^{10, 19}								X		

Procedure/Assessment Study Day	Dose Escalation and Dose Expansion Combination of Doxorubicin and NOX66 Treatment Period Cycles 1 - 3																
	Cycle 1 ¹						Cycle 2					Cycle 3					
	1	2	3-7	8	9 & 16	21	1	2	3-7	9 & 16	21	1	2	3-7	8	9 & 16	21
Assess disease status (CT and/or MRI) ²											X						
Vital signs		X						X					X				
Physical examination	X						X					X					

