11. The additional tests for hematology and serum chemistry on Days 9 and 16 are to assess any hematological or clinical laboratory tests for DLTs and/or require a dose reduction to 60 mg/m^2 or lower (37.5 mg/m^2 or 18.75 mg/m^2 based on serum bilirubin), or a delay in initiation of another cycle of the combination. These additional hematological and clinical laboratory tests should be performed at each cycle. Visit windows are ± 2 days of the scheduled visit.
12. During combination treatment cycles, NOX66 is administered on Days 1 to 7 and doxorubicin is administered on Day 2.
13. Doxorubicin (75 mg/m^2 or reduced dose) to be given on Day 2 of each 21-day cycle.
14. For Dose-Escalation Cohorts, PK samples will be obtained at pre-dose and at 1 and 2 hours post NOX66 on Day 2 Cycle 1. PK samples for idronoxil will be obtained on Day 2 of Cycles 2, 4 and 6 at pre-dose and 4 hours post dose. Additional PK samples for idronoxil will also be obtained pre-dose on Day 7 and at 8 or 12 hours after the last dose of NOX66 on Day 7 for those on a TID or BID regimens, respectively on Cycles 1, 3, and 5. For the Dose Expansion Cohort, PK samples for idronoxil will be obtained on Day 2 of Cycles 1, 2, 4, and 6 at pre-dose and at 4 hours post NOX66 and on Cycle 1 at 6 hours post NOX66. On Cycles 1, 3, and 5 PK samples are to be collected just prior to the morning dose of NOX66 on Day 7. For doxorubicin in the Dose Escalation Cohort, PK samples will be obtained at 0.5, 4 and 6 hours after the end of infusion on Day 2 Cycle 1 and at 0.5 and 4 hours at the end of infusion on Day 2, Cycles 2, 4 and 6. For doxorubicin in the Dose Expansion Cohort, PK samples will be obtained at 0.5, 4 and 6 hours after the end of infusion on Day 2 Cycle 1 and at 0.5 and 4 hours at the end of infusion on Day 2, Cycles 2, 4 and 6 ([Table 7](#)).
15. All patients who discontinue the study early for whatever reason after the first dose of NOX66, or during treatment cycles (Cycles 1-6), will be followed up within 28 days of discontinuation and submit to assessments detailed in the column of Cycle 6 Day 21/Early Termination. Patients who discontinue the study early during the follow-up period will complete a final visit with assessments detailed in the column of End of Study/Early Termination. Patients who complete the study in full will have an End of Study visit at Month 18.
16. Adverse events to be recorded up to 30 days after the last dose of NOX66 or doxorubicin, whichever is longer.

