14.3.5 LABORATORY SUMMARIES

Safety laboratory results will be summarized by dose group. At each scheduled laboratory collection, the laboratory result and the change from baseline in laboratory result will be summarized for each laboratory parameter. CTC grades will be assigned to laboratory results where they are defined, and the frequency and percentage of each CTC grade will be included in the summary.

Shift tables will be provided for change in CTC grade from baseline to end of study and from baseline to worst grade on study.

Brain type natriuretic peptide measurements will be summarized using descriptive statistics at baseline and at Cycles 1, 3, 5, and the end of Cycle 6 or Early Termination (if occurs prior to the end of Cycle 6). The number and percentage of patients with BNP laboratory values greater than 500 pg/mL and with BNP laboratory values between 100 and 500 pg/mL will be presented.

Blood levels of chemokines and cytokines will be summarized using descriptive statistics at baseline, Day 7 of Monotherapy period (only for Dose Escalation), at Cycle 3, and at the end of Cycle 6 or at Early Termination (if occurs prior to the end of Cycle 6).

Listings of genetic mutations at baseline and at end of Cycle 6 or Early Termination will be made.

Blood levels of ENOX2 will be summarized using descriptive statistics at baseline, at Cycle 3, and at the end of Cycle 6 or at Early Termination (if occurs prior to the end of Cycle 6). These levels will also be assessed in the same manner for patients in the Dose Escalation Cohorts, including those on Day 7 of Monotherapy period, if the samples are collected.

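### One laboratory shift table ends at a Month 18 sample about 13.9 months after Cycle 6, no end-of-treatment shift is planned, and worst grade has no on-treatment window (minor)

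*Combined protocol and SAP*

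**What the plan says.** Section 14.3.5 (Laboratory Summaries) states: "Shift tables will be provided for change in CTC grade from baseline to end of study and from baseline to worst grade on study". The synopsis repeats the rule and covers vital signs as well: "shift tables will be provided for CTC grades from baseline to end of study and from baseline to worst value on study".

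Section 14.3.5 also plans a by-visit summary: "At each scheduled laboratory collection, the laboratory result and the change from baseline in laboratory result will be summarized for each laboratory parameter". It adds that "CTC grades will be assigned to laboratory results where they are defined, and the frequency and percentage of each CTC grade will be included" in that summary.

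End of Study is a named visit. Table 4, footnote 15, says: "Patients who complete the study in full will have an End of Study visit at Month 18". Table 2 and Section 11.6.2.12 count that month from Cycle 1 Day 1, and Section 11.6.2.12 schedules laboratory tests at it. Table 4 schedules no haematology or chemistry at Months 6, 9, 12 or 15. The Table 2 footnote says that neither study drug is given in follow-up, but "other approved or investigational medication for sarcoma may be administered".

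During treatment, Section 11.4.2.4 places haematology and chemistry on Days 1, 9 and 16 of every cycle. Section 11.6.2.9 adds Cycle 6 Day 21 or Early Termination.

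Table 4, footnote 16, ends adverse event recording 30 days after the last dose of NOX66 or doxorubicin, whichever is longer.

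**The concern.** A shift table to a final time point normally shows where patients stood, relative to baseline, when they came off treatment. Read by the protocol's own defined visit, this one shows where completers stood more than a year later.

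The wording is hard to treat as loose shorthand. In the same Section 14.3.5, the BNP, cytokine, ENOX2 and genetic summaries stop at the end of Cycle 6 or Early Termination, and Section 14.3.8 does the same for echocardiography. A programmer following defined terms would take Month 18 for the laboratory shift.

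The second table has a related weakness. Because its worst grade covers the whole study, a late value caused by another cytotoxic drug can be counted in a NOX66 dose group.

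Laboratory assessments are among the primary safety endpoints (Section 11.1.1), so these tables should be attributable to the study treatment.

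**Working it through.** **1. Reproduce the plan's follow-up figure.** Section 8.1.2 gives about 14 months after Cycle 6.
- Treatment length ("which will consist of up to 6 x 21-day treatment cycles"): 6 × 21 = 126 days. At 365.25/12 = 30.44 days per month this is 4.14 months.
- Month 18 minus Cycle 6 Day 21: 18 − 4.14 = 13.86 months.
- Table 2 steps: 1.8 + 4 × 3 = 13.8 months.

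Both agree with the stated figure. From the last planned NOX66 day (Cycle 6 Day 7, day 112) the gap is 14.3 months. From the last planned doxorubicin dose (Cycle 6 Day 2, day 107) it is 14.5 months. These figures count Month 18 from Cycle 1 Day 1, as Section 8.1.2, Table 2 and Section 11.6.2.12 do. The synopsis counts the 15- and 18-month contacts from completion of Cycle 6, and this should be reconciled.

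**2. Count the samples that feed each summary.** A completer has 6 × 3 = 18 haematology and chemistry samples in the combination cycles, plus Cycle 6 Day 21, giving 19. All 19 enter the worst-grade table and the by-visit summaries. None of them is the end-of-study value if that means Month 18.

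**3. Follow two hypothetical completers, both Grade 0 at baseline.**

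| Patient | Cycle 6 Day 21 | Month 18 | Shift to end of study | Shift to worst grade |
|---|---|---|---|---|
| A: anaemia at end of treatment | Grade 2 | Grade 0 | 0 to 0 | 0 to 2 or worse |
| B: no grade above 0 on treatment; neutropenia on later chemotherapy | Grade 0 | Grade 3 | 0 to 3 | 0 to 3 |

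Patient A's toxicity is reported, but not as residual at end of treatment. Patient B's later event appears in both tables under the NOX66 dose group.

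**4. Ask who has an end-of-study value.** Under Table 4, footnote 15, patients who leave the study during treatment have the Cycle 6 Day 21/Early Termination assessments, and those who leave during follow-up have the End of Study/Early Termination assessments when they leave. Patients who only stop treatment stay on study (Section 11.2.2), so their end of study may still be Month 18. Section 14.3.1 imputes no laboratory values. Whether an Early Termination value counts as end of study in the shift table is not stated. If it does, the column mixes values near treatment with values more than a year off drug.

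**5. Illustrate survival to Month 18.** The plan gives no such figure. Assume exponential survival, so the share dead by Month 18 is 1 − 0.5^(18/median). Medians are those cited in Section 6.1.

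| Median survival (months) | Dead by Month 18 | Alive, of 34 |
|---|---|---|
| about 12 | 65% | 12 |
| 12.8 | 62% | 13 |
| 19 | 48% | 18 |
| 26.5 | 38% | 21 |

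The share dead is not the share with no table entry, because some patients will have had an exit sample.

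**The case against.** A reader might infer that the shift tables miss laboratory toxicity at the end of treatment. The documents do not support that. The sentence that plans the end-of-study shift also plans a worst-grade shift, which takes in every on-treatment sample including Cycle 6 Day 21. Grade frequencies are given at each scheduled collection. Clinically significant laboratory results are also adverse events (Section 11.4.2.4), and these are summarised by toxicity grade (Section 14.3.4).

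A reader might also infer that the end-of-study column holds only long survivors, with half or more of the patients missing. That is too strong. Early leavers have laboratory tests at exit, Sections 14.3.8 and 14.3.10 pair End of Study with Early Termination, and the full range of cited medians gives 38% to 65% dead by Month 18.

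It can further be said that Cycle 6 Day 21 is a poor toxicity endpoint. It falls 19 days after doxorubicin and 14 days after the last planned NOX66 dose, and Section 8.3.3 expects leukopenia to have usually recovered by the 21st day. That is a fair description of what the sample shows. But recovery or its absence is what an end-of-treatment shift is for. The worst-grade table cannot supply it, since it does not separate a passing nadir from a persistent abnormality. By-visit frequencies cannot supply it either, since they are not crossed with baseline grade.

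Finally, Section 14.3.12 leaves further presentation and data-handling rules to a later SAP, and dose escalation rests on Cycle 1 dose-limiting toxicities rather than this table. Both points stand and keep the severity low. They do not remove the problem, because Section 14.3.5 and the synopsis already state the end point, and a later SAP would inherit it.

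**Conclusion.** The point holds in a limited form and is minor. For completers, one of the two laboratory shift tables ends at a sample taken about 13.9 months after Cycle 6 Day 21, off both study drugs and possibly after other sarcoma therapy. No baseline-to-end-of-treatment shift is specified, the handling of Early Termination values is not stated, and worst grade has no on-treatment window.

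The loss is one clean cross-tabulation of residual toxicity, together with the chance that later therapy sets a patient's worst grade. The 13.9 months follows from the protocol's own schedule, counted from Cycle 1 Day 1. The 38% to 65% is an illustration that rests on exponential survival and on medians cited from other studies. It does not estimate how many table entries will be missing.

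**What to change.** In Section 14.3.5 and the synopsis:
- Replace the baseline-to-end-of-study shift with baseline to end of treatment. Define this as Cycle 6 Day 21/Early Termination, or the last value within 30 days after the last dose of NOX66 or doxorubicin, matching the adverse event window in Table 4, footnote 16. The 30-day alternative also serves patients who stop treatment but remain in follow-up.
- Define worst grade over the same window.
- Report Month 18 and follow-up exit values by visit only.

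The synopsis sentence also covers vital signs, so the change should apply to both. The SAP that Section 14.3.12 requires before the expansion cohort opens can carry the same definitions.

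The cost is wording. No new samples are needed. The downside is that late laboratory changes will appear only in the by-visit table.

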14.3.6 VITAL SIGNS

Vital signs will be summarized by dose group. Descriptive statistics will be provided for each vital sign at each visit and for the change from baseline to that visit. For vital signs with an associated CTC grade, the summaries will include the number and percent of patients at each grade.

14.3.7 ECG PARAMETERS

For each ECG parameter (PR, RR, QRS, and QT intervals, and QT interval corrected for heart rate using QTcF intervals where the QT intervals corrected for heart rate by Fridericia's formula [QTcF = QT/(RR)^{2/3}]), the parameter and the change from baseline in that parameter will be summarized at all time-points where an ECG is collected. Where triplicate ECG measurements are available, the descriptive statistics will be calculated using the arithmetic average of the three raw measurements. Holter monitoring will not assess ECG intervals but will provide information on cardiac rate and rhythms.

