--	--

	
Cardiac Monitoring
 
Day 1 Monotherapy: Triplicate 12-lead ECGs will be obtained after 5 minutes of rest in the supine position at -0.75, -0.5 and -0.25 hours prior to administration of NOX66 and at 1, 2, 5, and 8 hours after the first dose of NOX66 monotherapy. Additional ECGs in triplicate may be taken more frequently if QTc intervals exceed 500 ms during the study. The ECG parameters, QT, QT interval adjusted for the patient's heart rate by Fridericia's method (QTcF), PR, QRS, and RR intervals; heart rate; and T-wave amplitude, as well as any change from baseline, will be assessed and the relationship between NOX66 blood concentrations may be explored to determine if there is an effect on QTcF.
 
Day 7 Monotherapy: Triplicate 12-lead ECGs will be obtained after 5 minutes of rest in the supine position at -0.75, -0.5 and -0.25 hours prior to administration of NOX66 and at 1, 2, 5, and 8 hours after the morning dose of NOX66. Holter monitoring will be used to record cardiac activity from 8 to 24 hours after the last morning dose of NOX66 monotherapy in each cohort.
 
Cycle 1 Day 2: Triplicate 12-lead ECGs will be obtained after 5 minutes of rest in the supine position at -0.75, -0.5 and -0.25 hours prior to administration of NOX66 and at 1, 2, 5, and 8 hours after the morning dose of NOX66. Cardiac activity will be recorded with Holter monitoring from 8 to 24 hours after administration of NOX66.
 
Cycles 2 to 6 Day 2 (combination of NOX66 and doxorubicin): Triplicate 12-lead ECGs will be obtained after 5 minutes of rest in the supine position at -0.25 hours prior to and at 1, 2, 5, and 8 hours post application of NOX66.
 
Months 6, 9 and 12: Triplicate 12-lead ECGs will be obtained after 5 minutes of rest in the supine position.
 
Echocardiography will be conducted at Screening, Day 1 of Cycles 3 and 5, and at the end of Cycle 6 or Early Termination (if the patient discontinues prior to 6 cycles).

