14.3.9 PHARMACOKINETIC ANALYSES

Blood concentration of idronoxil and metabolites will be summarized by collection time for each dose group using descriptive statistics. Separate summaries will be provided for idronoxil blood concentrations collected on Days 1 and 7 of idronoxil monotherapy, and from pre-dose to 4 hours post dose on Day 2 of Cycles 1 to 6. Trough values will also be assessed on Days 7 and 8 of Cycles 1, 3 and 5. Blood concentrations of idronoxil after monotherapy and in combination with doxorubicin will be compared.

Plasma concentrations of doxorubicin and doxorubicinol will be summarized by collection time for each dose group using descriptive statistics.

Pharmacokinetic parameters will be summarized by descriptive statistics for each dose group for idronoxil alone on Days 1 and 7. Graphical methods may be used to assess the relationship between idronoxil and doxorubicin concentrations and QTc values and other toxicities of interest.

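### Section 14.3.7 names Fridericia's cube-root correction but prints an exponent of 2/3, so QTcF programmed as printed would carry heart-rate changes into the ECG summaries

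*Combined protocol and SAP*

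**What the plan says.** Section 14.3.7 sets out the ECG parameters to be analysed: PR, RR, QRS, QT and rate-corrected QT. It defines the last of these as the "QT interval corrected for heart rate using QTcF intervals where the QT intervals corrected for heart rate by" Fridericia's formula, and the formula follows in brackets: "Fridericia's formula [QTcF = QT/(RR)^{2/3" (the closing brackets are cut off in this quotation). For every parameter, "the parameter and the change from baseline in that parameter will be summarized at all time-points where an ECG is collected". Triplicate readings are averaged first.

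The synopsis (Cardiac Monitoring) names the same method without a formula: "QT interval adjusted for the patient's heart rate by Fridericia's method (QTcF". The abbreviation list does likewise. Section 14.3.7 is therefore the only place where a QTcF formula appears.

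QTcF is used in these places:

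- The synopsis (Statistical Methods, Safety) adds worst values: "A similar analysis will be provided for the worst value of each ECG parameter on study".
- The synopsis (Cardiac Monitoring) says that "the relationship between NOX66 blood concentrations may be explored to determine if there is an effect on QTcF".
- Section 14.3.9 says: "Graphical methods may be used to assess the relationship between idronoxil and doxorubicin concentrations and QTc values".
- Section 11.1.1 lists ECG parameters among the primary (safety) endpoints.
- The synopsis also allows extra triplicate ECGs when QTc is above 500 ms, without saying which QTc value is meant.

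**The concern.** Fridericia's correction is, by definition, division by the cube root of RR. An exponent of 2/3 belongs neither to it nor to the usual square-root alternative (Bazett, exponent 1/2). The section therefore defines an analysed variable in two incompatible ways. It does not give the unit of RR, and it does not say whether QTcF is calculated in the analysis or copied from the ECG report.

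The purpose of the correction is to remove heart rate from QT. An exponent that is too large over-corrects: faster rates look like QTcF prolongation and slower rates like shortening. If heart rate shifts during treatment, the change-from-baseline tables could show a QT signal that is not there, or hide one that is.

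**Working it through.** **Inputs.** From section 14.3.7: the named method (Fridericia, exponent 1/3) and the printed exponent (2/3). Assumed, because the documents give no ECG values: RR = 60/HR in seconds, heart rates of 50 to 100 bpm, and a true QTcF of 410 ms.

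**Can the printed exponent be reconciled with the name?** No. Fridericia gives 1/3 and Bazett 1/2. Changing the unit does not help: at 75 bpm with RR = 800 ms, QT is 380.6 ms and 380.6/800^(2/3) = 4.42, which is not a usable QTcF. Seconds is the only unit that gives plausible values.

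**What the printed formula returns.** On Fridericia's own premise, QT = QTcF × RR^(1/3). Then

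QT/RR^(2/3) = QTcF × RR^(−1/3) = QTcF × (HR/60)^(1/3).

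Uncorrected QT equals QTcF × (HR/60)^(−1/3). The printed version therefore depends on rate exactly as strongly as uncorrected QT, with the sign reversed. The printed and cube-root forms agree only at 60 bpm.

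**Values for a true QTcF of 410 ms:**

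| HR (bpm) | RR (s) | QT (ms) | QT/RR^(1/3) | QT/RR^(2/3) | Factor |
|---|---|---|---|---|---|
| 50 | 1.200 | 435.7 | 410 | 385.8 | 0.941 |
| 60 | 1.000 | 410.0 | 410 | 410.0 | 1.000 |
| 65 | 0.923 | 399.2 | 410 | 421.1 | 1.027 |
| 75 | 0.800 | 380.6 | 410 | 441.7 | 1.077 |
| 85 | 0.706 | 365.1 | 410 | 460.5 | 1.123 |
| 90 | 0.667 | 358.2 | 410 | 469.3 | 1.145 |
| 100 | 0.600 | 345.8 | 410 | 486.1 | 1.186 |

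**Change from baseline:**

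- 75 to 85 bpm, no QT effect: 460.5 − 441.7 = +18.8 ms. Uncorrected QT moves by about −15.6 ms over the same step.
- 75 to 65 bpm, no QT effect: 421.1 − 441.7 = −20.6 ms.
- True rise of 20 ms (410 to 430) with a fall from 75 to 65 bpm: 441.66 to 441.63, a change of −0.03 ms.

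**The 500 ms level.** If that check used values from the printed formula, a reading of 500 ms would correspond to a true QTcF of 500 × (60/HR)^(1/3): 531 ms at 50 bpm, 454 ms at 80 bpm and 422 ms at 100 bpm.

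**The case against.** The strongest objection is that the distortion may never occur.

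- The text was read from a PDF by a program, and a raised fraction is easily misread. No second formula corroborates the 2/3.
- Fridericia is named consistently in the synopsis, the abbreviation list and section 14.3.7, so a statistician may well implement the cube root regardless of what is printed.
- Section 14.3.12 leaves further methods to a SAP to be approved before the expansion cohort opens, so the slip could be caught there. RR units and the source of QTcF are arguably details for that document.
- The 500 ms provision suggests that a QTc value is available at the time of recording, independent of section 14.3.7.
- Nothing inferential depends on QTcF, and because QT and RR are also collected and summarised, the standard value can be recomputed.
- The sizes are illustrative, and the case of a true +20 ms reading as zero was chosen so that the two terms cancel.

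Most of this stands, and it limits the finding. The harm is conditional on someone programming from the printed text, the exponent needs checking at source, and the cancelling example shows what is possible, not what to expect. The contradiction itself remains. As supplied, the exponent is an explicit 2/3. It sits in the statistical methods as the definition of an analysed variable, and no separate SAP or programming specification was available that corrects it.

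**Conclusion.** The point holds. The only QTcF formula in the plan contradicts the method it is named after. Followed as written, it would inflate QTcF by about 8% at 75 bpm and 19% at 100 bpm, lower it by about 6% at 50 bpm, and turn a 10 bpm change around 75 bpm into a spurious change of roughly 20 ms. These figures rest on RR in seconds, QT proportional to RR^(1/3), and an assumed true QTcF of 410 ms. The percentages do not depend on the 410 ms.

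The reach is limited to the QTcF summaries by time point, change from baseline and worst value, the optional concentration plots, and possibly the 500 ms check if it used this formula. It does not touch MTD determination, any hypothesis test or the sample size. It should be fixed, since ECG parameters are among the primary safety endpoints. If the source PDF shows 1/3, the point about the exponent falls away. If standard Fridericia values are what is programmed or reported, it is a text error only.

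**What to change.** 1. Check the exponent in section 14.3.7 against the source PDF.
2. If it is 2/3 there, print QTcF = QT/(RR)^(1/3), with RR in seconds.
3. State in one sentence whether QTcF is derived in the analysis or taken from the ECG report.
4. Carry the same definition into the SAP and the programming specifications.

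The cost is one exponent, one unit and one sentence. No new data are needed. Any QTcF values already derived with the printed formula can be recalculated from the stored QT and RR.
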